5.3 Drug Administration

5.3.1 Premedication

Prior to each dose of study drug, in order to reduce the risk of experiencing an IRR, patients will receive the following premedications at least 60 minutes prior to the infusion:

- Intravenous dexamethasone (10 mg) or equivalent;
- Oral paracetamol/acetaminophen (500 mg) or equivalent;
- Intravenous H2 blocker (e.g., ranitidine 50 mg, famotidine 20 mg, or equivalent other H2 blocker dose);
- Intravenous H1 blocker: diphenhydramine 50 mg (or equivalent other IV H1 blocker available at the study site). Hydroxyzine or fexofenadine 25 mg per os (PO, orally) or cetirizine 10 mg PO may be substituted for any patient who does not tolerate IV diphenhydramine or other IV H1 blocker.

Patients will be started on the above premedication regimen. However, modifications may be made to the premedication regimen after consultation with the medical monitor either due to a patient's inability to tolerate one or more of the premedications or to the occurrence of IRRs unresponsive to slowing of the infusion rate.

- If a patient is having difficulty tolerating the steroid premedication regimen (e.g., patient develops uncontrolled hyperglycemia, altered mental status, or other complication), then lowering of the steroid premedication may be allowed for that patient after consultation with the medical monitor.
- If after consultation with the medical monitor, it is agreed that an individual patient's steroid premedication will be lowered, then the following steps **must be followed**:
 - 1) If the current steroid dosage is 10 mg intravenous dexamethasone or equivalent, then the patient may be lowered in increments no greater than 2.5 mg intravenous dexamethasone or equivalent.
 - 2) After each incremental lowering below 10 mg intravenous dexamethasone or equivalent, the patient must receive three consecutive intravenous doses of patisiran without IRR and continued signs or symptoms of steroid intolerance before further reductions in steroid premedications.
 - 3) The premedication steroid dosage should not be reduced below 5 mg intravenous dexamethasone or equivalent.

Alternatively, if a patient experiences an IRR when 10 mg or less of intravenous dexamethasone or equivalent is used as the steroid premedication, then proceed to [Section 5.9](#).

Further details (including a table of equivalent premedications) can be found in the patisiran (ALN-TTR02) Pharmacy Manual.

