5.3.2 Study Drug Administration

Patients who are randomized into the active treatment group will receive 0.3 mg/kg patisiran once every 21 days (\pm 3 days). Patients who are randomized into the control group will receive placebo (normal saline 0.9%) once every 21 days (\pm 3 days).

The body weight that was obtained during the previous visit must be used to calculate the dose of study drug. In the event that the body weight obtained on the previous dosing day is not available, the body weight obtained pre-dose on the dosing day can be used for the dose calculation. Patients who weigh 105 kg or more will receive patisiran dosing based on an assumption of a body weight of 104 kg.

Study drug (either patisiran or placebo) will be administered under the supervision of the unblinded site personnel, as a 70-minute IV infusion (approximately 1 mL/minute for the first 15 minutes followed by approximately 3 mL/minute for the remainder of the infusion). The study drug will be administered via a controlled infusion device with an extension set containing a 1.2 micron filter supplied by Alnylam or designee. Infusion products must not contain polyvinyl chloride, di(2-ethylhexyl)phthalate (PVC, DEHP). As described in [Section 4.4.3](#), the tubing and the lines will be covered so that it will not be possible to detect a difference in active versus placebo drug.

- If the patient experiences an IRR the infusion time may be extended up to 3 hours in the event of a mild or moderate IRR.
 - 1) If the patient experiences a mild or moderate IRR that resolves by slowing the infusion rate then no further premedication changes are recommended.
 - 2) If the patient experiences a severe IRR, then study drug administration will not be resumed until the case is discussed with the medical monitor (see [Section 5.9](#)).
- If the infusion time for a patient was extended due to an IRR, that modified infusion duration should be continued throughout the duration of the study for that particular patient. Returning the patient's infusion duration to 70 minutes will require a discussion with the medical monitor.
- For the first 3 infusions of study drug on this study, the patient's infusion site should be assessed for signs of any localized reaction during the infusion and for 30 minutes after the end of the infusion, and the patient will remain at the clinical site for 1 hour following completion of dosing.

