Tabulations by SOC and preferred term will be produced for the following: all AEs; AEs related to treatment; severe AEs; AEs leading to infusion interruption; AEs leading to drug delay; AEs leading to treatment discontinuation; AEs leading to study withdrawal; and SAEs. Separate tables will be provided summarizing signs and symptoms of IRRs (overall and by premedication regimen) and AEs related to premedication (overall and by premedication regimen) by SOC and preferred term. The incidence and frequency of AEs and IRRs over time will also be summarized by SOC and preferred term. Adverse events and AEs related to treatment will also be tabulated by preferred term in decreasing order in frequency in the patisiran arm. Adverse events and SAEs will also be summarized by SOC and preferred term for the cardiac subpopulation.

Separate tables will present AE incidence rates by maximum relationship to study drug and by maximum severity. Patients who report multiple occurrences of the same AE (preferred term) will be classified according to the most related or most severe occurrence, respectively.

AEs mapping to the standardized MedDRA query (SMQ) Depression and Suicide/Self-injury will be summarized by preferred term. Adverse events mapping to the SMQ Drug Related Hepatic Disorder will be summarized by SOC and preferred term. Adverse events mapping to the SMQ Malignant or Unspecified Tumors will be summarized by high level term and preferred term. Other SMQs or AE groupings may be evaluated.

All AEs will be presented in patient data listings. Separate listings will be provided for death, SAEs, AEs leading to treatment discontinuation, AEs leading to study withdrawal, IRRs, AEs related to premedications, AEs related to study procedures, and AEs mapping to the SMQ as described above. A listing of patients who underwent liver transplant will also be provided.

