4.6.6. Premedication

All patients received premedication in order to reduce the potential of an IRR. The original premedication regimen as outlined below was used at the start of the study. A subset of patients experienced AEs suspected to be related to steroids (e.g., flushing) and were transitioned to a modified premedication regimen, with a reduced dose of corticosteroid to mitigate these events, as sanctioned in the protocol. After observing that the subset of patients tolerated the lower corticosteroid dose with no increase in IRRs, the protocol was amended (Amendment 5.0) to transition the rest of the patients to the modified premedication regimen (see below).

The following original premedication regimen was used prior to protocol amendment 5.0:

- Dexamethasone 8 mg PO or equivalent administered the evening before dosing and 20 mg PO at least 60 minutes prior to the start of the infusion of patisiran;
- Paracetamol 500 mg PO or equivalent administered the evening before dosing and at least 60 minutes prior to the start of the infusion of patisiran;
- H2 blocker PO (e.g., ranitidine 150 mg or famotidine 20 mg or equivalent other H2 blocker dose) administered the evening before dosing and at least 60 minutes prior to start of the infusion of patisiran; and
- H1 blocker PO, 10 mg cetirizine or equivalent (hydroxyzine 25 mg or fexofenadine could be substituted if patient did not tolerate cetirizine) administered the evening before dosing and at least 60 minutes prior to start of the infusion of patisiran.

The following reduced premedication regimen was instituted for all patients with protocol amendment 5.0:

- Dexamethasone 10 mg IV or equivalent, administered at least 60 minutes prior to the start of the infusion of patisiran;
- Paracetamol 500 mg PO or equivalent at least 60 minutes prior to the start of the infusion of patisiran;
- H2 blocker IV (e.g., ranitidine 50 mg, famotidine 20 mg, or equivalent other H2 blocker dose) at least 60 minutes prior to the start of the infusion of patisiran; and
- H1 blocker IV, diphenhydramine 50 mg (or equivalent other IV H1 blocker available at the study site) at least 60 minutes prior to the start of the infusion of patisiran. Hydroxyzine 25 mg PO or fexofenadine 30 or 60 mg PO or cetirizine 10 mg PO could be substituted for any patient who did not tolerate IV diphenhydramine or other IV H1 blocker.

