A drug exposure table summarizing the treatment duration under “original” and “reduced” regimens will be provided. A patient who switches from “original” to “reduced” regimen during treatment will be counted in both categories.

Premedications will be coded using the WHO Drug Dictionary (March 2015 or later). Results will be tabulated by anatomic therapeutic class (ATC) and preferred term.

Premedication data will be listed. In addition, a listing will be provided to present the durations of study drug exposure under original regimen and reduced regimen for each patient.

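### The tables of infusion-related reactions and premedication-related AEs by premedication regimen set side by side columns that differ in infusion order, patient selection and exposure, and so can mislead in either direction

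*SAP*

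**What the plan says.** SAP 4.6.2 (Adverse Events): "Separate tables will be provided summarizing signs and symptoms of IRRs (overall and by premedication regimen"). AEs related to premedication get the same overall and by-regimen split. The section counts a patient once for a given event and makes event counts optional. It also plans a summary of IRRs over time, which is not crossed with regimen. It does not say how an event is assigned to a regimen, what the by-regimen denominator is, or how infusion number is handled.

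SAP 4.6.6 (Premedication) gives the history: "The original premedication regimen as outlined below was used at the start of the study". Then: "A subset of patients experienced AEs suspected to be related to steroids (e.g., flushing) and were transitioned to a modified premedication regimen". Once that subset had been observed on the lower dose, "the protocol was amended (Amendment 5.0) to transition the rest of the patients to the modified premedication regimen". The section plans an exposure table by regimen ("A drug exposure table summarizing the treatment duration under" the two regimens) and says that a patient who changes "regimen during treatment will be counted in both categories".

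The current protocol, section 5.3.1, lists the reduced regimen and says: "Patients will be started on the above premedication regimen". Protocol 5.3.2 says of an infusion extended because of an IRR: "that modified infusion duration should be continued throughout the duration of the study for that particular patient". Going back to 70 minutes requires a discussion with the medical monitor.

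**The concern.** A reader of the study report will look along the row and compare the regimens. Four documented features make that unsafe:

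- **Order.** Within switchers, every original-regimen infusion comes before every reduced-regimen infusion.
- **Selection.** The first switchers were chosen because of suspected steroid AEs. The events that prompted the switch occurred on the original regimen, so in the premedication-AE table they fall in that column by construction.
- **Carry-over.** A patient whose infusion was lengthened after a reaction normally enters the reduced period on the longer infusion.
- **Exposure.** With patients counted once, the percentage grows with the number of infusions in the period, and that number differs between regimens.

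Patients who started under the amended protocol have their early infusions in the reduced column and nothing in the original one. At stake is any statement in the report about IRRs or steroid-related events under the lower premedication dose.

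**Working it through.** The plan states no IRR rate, switch time or number of switchers, so there is no figure to reproduce. The check asks whether the crude table can show a difference when there is none, and in which direction.

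**From the documents.** Dosing is every 21 days from Day 0 to Day 546: 546/21 + 1 = 27 planned infusions. Each patient counts once per event.

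**Assumed, for illustration only.** IRR risk is 5% at each of infusions 1-3 and 1% at each later one, independent between infusions and identical under both regimens. All patients switch after infusion s, with s at least 3. There is no dropout and no carry-over.

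**Formulas.**

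- Patients with an IRR, original: 1 − 0.95^3 × 0.99^(s−3)
- Patients with an IRR, reduced: 1 − 0.99^(27−s)
- Mean risk per infusion, original: (3 × 5% + (s−3) × 1%)/s; reduced: 1%

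| Switch after | Patients, original | Patients, reduced | Per infusion, original | Per infusion, reduced |
|---|---|---|---|---|
| 4 | 1 − 0.95^3 × 0.99 = 15.1% | 1 − 0.99^23 = 20.6% | 16%/4 = 4.0% | 1.0% |
| 7 | 1 − 0.95^3 × 0.99^4 = 17.6% | 1 − 0.99^20 = 18.2% | 19%/7 = 2.7% | 1.0% |
| 12 | 1 − 0.95^3 × 0.99^9 = 21.7% | 1 − 0.99^15 = 14.0% | 24%/12 = 2.0% | 1.0% |

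With no regimen effect, the patient percentages favour the original regimen for an early switch and the reduced regimen for a later one. Declining risk is not needed. At a constant 1% and a switch after infusion 9, the figures are 1 − 0.99^9 = 8.6% against 1 − 0.99^18 = 16.5%, from unequal exposure alone.

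**A true increase.** Let the reduced regimen carry 1.5 times the risk, 1.5% per infusion. After a switch at 12 the table shows 1 − 0.985^15 = 20.3% against 21.7%, so the increase is hidden. After a switch at 4 it shows 1 − 0.985^23 = 29.4% against 15.1%, so it is exaggerated.

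**Patients who start on the reduced regimen.** Under the same risks and no regimen effect, such a patient has an IRR with probability 1 − 0.95^3 × 0.99^24 = 32.6%, all of it in the reduced column. The more of them there are, the higher that column.

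**Why an infusion denominator alone is not enough.** It removes the exposure problem: at constant risk both columns read 1.0%. It does not remove order. Under the declining risks, the crude per-infusion figures run from 4.0% against 1.0% to 2.0% against 1.0% with no true difference. Only a comparison at similar infusion numbers deals with both.

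**The case against.** The strongest reply is that the table is descriptive. SAP 4.6 says so of all safety summaries, and no test or claim comparing regimens is planned. The tables are by arm, and placebo patients receive the same premedication, so there is a concurrent contrast within each regimen. The SAP also plans IRR listings, a listing of each patient's exposure under each regimen, infusion durations and the over-time summary. Banding by infusion number will leave sparse cells.

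Most of this is fair, and it limits the severity. It does not make the columns comparable. The placebo contrast shows general time trends but cannot separate a fall in IRR risk specific to patisiran from a regimen effect. The over-time summary is not split by regimen, and listings leave the reader to build the comparison.

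Four stronger readings are tempting, and the documents do not support them:

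- *The original regimen always came first.* This is true of switchers only; under the current protocol patients start on the reduced regimen.
- *Switchers are counted in both columns of the IRR table.* That rule is written for the exposure table in SAP 4.6.6. It is a natural reading for the IRR table but is not stated there.
- *This table is the evidence for the SAP's remark that IRRs did not increase on the lower dose.* That observation concerned the early switchers and preceded the amendment.
- *A patient who reacts always keeps a slower infusion.* Extension is optional, and it can be reversed after discussion with the medical monitor.

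**Conclusion.** The crude by-regimen tables can differ between regimens when the regimens do not differ, and can hide or exaggerate a real difference. A reader might infer that they must make the reduced regimen look safer. The documents do not show that: they give no IRR rates, no switch times and no evidence that risk falls with repeated infusions, and under one set of assumed risks the direction reverses with the switch point alone (21.7% against 14.0% after infusion 12; 15.1% against 20.6% after infusion 4). The size and direction in this trial are therefore unknown. What rests on the documents alone is the lack of comparability: order within switchers, selection of the first switchers, lengthened infusions carried forward and unequal infusion counts. The effect is confined to a descriptive safety display and any sentence written from it. Primary and secondary efficacy inference is untouched. The point is minor, and worth acting on because the change is cheap.

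**What to change.** In SAP 4.6.2:

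- Assign each IRR to the regimen given at that infusion. Say where infusions belong when the steroid dose was individually lowered or raised under Protocol 5.3.1 or 5.9.
- Report IRRs per infusion, by arm and regimen, within infusion-number bands (for example 1-3, 4-9, and 10 or more).
- Show original-only, switcher and reduced-only patients separately.
- Flag infusions already lengthened because of an earlier IRR.
- Keep the crude by-regimen patient table if wanted, labelled as descriptive and not comparative. For premedication-related AEs, add a note that the events prompting the first switches fall under the original regimen.

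The cost is a few lines of SAP wording and one restructured table, built from infusion, premedication and IRR records that the SAP already summarises or lists. The downside is smaller counts per cell.

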4.6.3. Laboratory Data

Clinical laboratory values will be expressed in SI units.

Summary data for each laboratory parameter will be presented for each continuous clinical laboratory parameter (including hematology, serum chemistry, coagulation studies and thyroid and liver function tests). Descriptive statistics will be presented for the actual values, change from baseline, and percent change from baseline by visit.

For each continuous laboratory parameter, results will be categorized as low, normal, or high based on the laboratory normal ranges. Shift tables will be employed to summarize the baseline category versus the “worst” post-baseline category, where the “worst” post-baseline category will be based on the maximum difference (in absolute value) from the upper or lower limits of the normal range.

A listing will be produced for all patients with abnormal liver function tests defined as an ALT > 3×ULN, AST > 3×ULN, and total bilirubin > 2×ULN at any time point.

A table will be produced to summarize the number and percentage of patients in each of the below categories at any post-baseline time point.

- ALT > 1 & ≤ 3, > 3 & ≤ 5, > 5 & ≤ 10, > 10 & ≤ 20, > 20 ×ULN,
- AST > 1 & ≤ 3, > 3 & ≤ 5, > 5 & ≤ 10, > 10 & ≤ 20, > 20 ×ULN,
- ALT or AST > 1 & ≤ 3, > 3 & ≤ 5, > 5 & ≤ 10, > 10 & ≤ 20, > 20 ×ULN,
- ALP > 1.5 ×ULN,
- Total Bilirubin > 1.5 & ≤ 2, > 2 & ≤ 3, > 3 & ≤ 5 and > 5 ×ULN,
- Total Bilirubin > 2 ×ULN concurrent with ALT or AST > 3 ×ULN.

A shift table from baseline to worst post-baseline for ALT, AST, and total bilirubin will also be provided. In separate figures, the peak total bilirubin (at any time post-baseline) will be plotted against the peak AST, the peak ALT, and the peak AST or ALT levels at any time post-baseline.

For hematology and blood chemistry, summary tables of potentially clinically significant abnormalities will be provided. The results may also be graded according to the NCI CTCAE Version 4.0 or above. A shift summary of baseline to maximum post-baseline CTCAE grade may be presented, as appropriate.

The estimated glomerular filtration rate (eGFR, mL/min/1.73 m²) will be categorized as below: ≥ 90; 60-89; 30-59; 15-29 and < 15. A shift summary of baseline to worst post-baseline eGFR category will be presented.

All laboratory data will be provided in data listings. Out-of-range laboratory results will be identified in the listings.

4.6.4. Vital Signs and Physical Examination

Descriptive statistics will be provided for vital signs, including blood pressure, pulse rate, oral body temperature and respiration rate.

Vital sign measurements will be presented for each patient in a data listing.

All physical examination findings will be presented in a by-patient data listing. Abnormal physical examination findings will be presented in a separate listing.

4.6.5. Electrocardiogram

Electrocardiogram (ECG) findings will include rhythm, ventricular rate, PR interval, QRS duration, QT interval, and QTc interval. For each time point, the results will be the average of measurements from the triplicate ECGs for each patient recorded at that time point. Descriptive statistics will be provided for each measure over time. Change from pre-dose to each post-dose assessment will also be summarized. The number and percentage of patients with normal, abnormal, and clinically significant abnormal results at baseline and each study visit will also be summarized.

Corrected QT interval (QTc) will be calculated using both Fridericia's and Bazett's correction formula. Categorical analyses of the QTcF/QTcB data will be conducted and summarized as follows:

- The number and percentage of patients with maximum increase from baseline in QTcF/QTcB (< 30, 30 – 60, > 60 ms)
- The number and percentage of patients with maximum post-baseline QTcF/QTcB (< 450, 450 – < 480, 480 – 500, > 500 ms)

All ECG data for each patient will be provided in a data listing. A separate listing will be provided for patients with any post-baseline value > 500ms or an increase from baseline > 60 ms.

4.6.6. Premedication

All patients received premedication in order to reduce the potential of an IRR. The original premedication regimen as outlined below was used at the start of the study. A subset of patients experienced AEs suspected to be related to steroids (e.g., flushing) and were transitioned to a modified premedication regimen, with a reduced dose of corticosteroid to mitigate these events, as sanctioned in the protocol. After observing that the subset of patients tolerated the lower corticosteroid dose with no increase in IRRs, the protocol was amended (Amendment 5.0) to transition the rest of the patients to the modified premedication regimen (see below).

The following original premedication regimen was used prior to protocol amendment 5.0:

- Dexamethasone 8 mg PO or equivalent administered the evening before dosing and 20 mg PO at least 60 minutes prior to the start of the infusion of patisiran;
- Paracetamol 500 mg PO or equivalent administered the evening before dosing and at least 60 minutes prior to the start of the infusion of patisiran;
- H2 blocker PO (e.g., ranitidine 150 mg or famotidine 20 mg or equivalent other H2 blocker dose) administered the evening before dosing and at least 60 minutes prior to start of the infusion of patisiran; and
- H1 blocker PO, 10 mg cetirizine or equivalent (hydroxyzine 25 mg or fexofenadine could be substituted if patient did not tolerate cetirizine) administered the evening before dosing and at least 60 minutes prior to start of the infusion of patisiran.

The following reduced premedication regimen was instituted for all patients with protocol amendment 5.0:

- Dexamethasone 10 mg IV or equivalent, administered at least 60 minutes prior to the start of the infusion of patisiran;
- Paracetamol 500 mg PO or equivalent at least 60 minutes prior to the start of the infusion of patisiran;
- H2 blocker IV (e.g., ranitidine 50 mg, famotidine 20 mg, or equivalent other H2 blocker dose) at least 60 minutes prior to the start of the infusion of patisiran; and
- H1 blocker IV, diphenhydramine 50 mg (or equivalent other IV H1 blocker available at the study site) at least 60 minutes prior to the start of the infusion of patisiran. Hydroxyzine 25 mg PO or fexofenadine 30 or 60 mg PO or cetirizine 10 mg PO could be substituted for any patient who did not tolerate IV diphenhydramine or other IV H1 blocker.

A drug exposure table summarizing the treatment duration under “original” and “reduced” regimens will be provided. A patient who switches from “original” to “reduced” regimen during treatment will be counted in both categories.

Premedications will be coded using the WHO Drug Dictionary (March 2015 or later). Results will be tabulated by anatomic therapeutic class (ATC) and preferred term.

Premedication data will be listed. In addition, a listing will be provided to present the durations of study drug exposure under original regimen and reduced regimen for each patient.

